5.5. Handing protocol deviations

A protocol deviation is defined as a failure to adhere to the protocol such as errors in applying the inclusion/exclusion criteria, the incorrect intervention being given, incorrect data being collected or measured, follow-up visits outside the visit window or missed follow-up visits. We will apply a strict definition of the ITT (intention to treat) principle and will include all participants as per the ITT population described in section 5.3 in the analysis, in some form, regardless of deviation from the protocol.² This does not include those participants who have specifically withdrawn consent for the use of their data in the first instance; however, these outcomes will be explored as per other missing responses.

5.6. Unblinding

In this study, the unblinding of the Trial Statistician to the intervention code will take place once the database is locked for final analysis, or the data has been downloaded for a planned analysis, unless the DMC request that they review the interim data with knowledge of the intervention groups or the DMC request to be unblinded at an interim analysis.

6. Trial population

6.1. Recruitment

A flow diagram (as recommended by CONSORT³) will be produced to describe the participant flow through each stage of the trial. This will include information on the number (with reasons) of losses to follow-up (drop-outs and withdrawals) over the course of the trial. A template for reporting will be given in a separate template report.

6.2. Baseline characteristics

The trial population will be tabulated as per the template report document. Categorical data will be summarised by number of participants, counts and percentages. Continuous data will be summarised by the number of participants, mean and standard deviation if deemed to be normally distributed or number of participants, median and interquartile range if data are skewed, and ranges if appropriate. Tests of statistical significance will not be undertaken, nor confidence intervals presented.⁴

Baseline characteristics will be reported by Letrozole versus clomifene and metformin versus placebo as well as the four treatment arms in the following way:

- A) letrozole plus metformin
- B) clomifene plus metformin
- C) letrozole plus placebo
- D) clomifene plus placebo

7. Intervention(s)

7.1. Description of the intervention(s)

A template for reporting information on the intervention(s) will be given in a separate template report.

7.2. Adherence to allocated intervention

A cross-tabulation of allocated intervention by the adherence categories stated in section 5.4 will be produced (proportions and percentages). A template for reporting adherence will be given in a separate template report.

8. Protocol deviations

Frequencies and percentages by group will be tabulated for the protocol deviations as per separate template report.

9. Analysis methods

Intervention groups will be compared using regression models to adjust for all covariates as specified in section 9.1, where possible.

Output for the analysis will be reported via the comparisons as mentioned in section 4.12 Trial comparisons.

9.1. Covariate adjustment

Both group allocations (as a result of the double randomisation required by the factorial design) will be included in all analysis models (for comparisons A and B only as for C, D and E this would not be possible as we are only looking at one of the randomisations. See section 4.12 Trial comparisons for details on the comparisons); no interaction of treatment effect is assumed in the first instance but this will be explored through supportive analyses (section 9.10).

In the first instance, intervention effects between groups for all outcomes will be adjusted for the minimisation parameters listed in section 4.6 in the same form as entered into the minimisation algorithm, i.e. categorical variables such as age will remain as such in the model, rather than converting them to the continuous form (as this creates a problem downstream in terms of presentation of the subgroup analyses). Randomising centre will be included as a random intercept in the model, and all other factors as fixed effects (with the exception of time to event outcomes where centre will be regarded as a shared frailty).

A mixed effects binomial regression model will be used to calculate the risk difference (identity link) and relative risk (log link) with 95% confidence intervals for the primary outcome (live birth \geq 34 weeks), adjusting for the randomisation variables listed in section 4.6. If the binomial model fails to converge then, in the first instance, a Poisson regression model with randomising centre as a random effect and robust standard errors will be used to estimate the relative risk. In the case that the Poisson regression model still does not converge, randomising centre will be removed and the log-binomial model will be refit for just fixed effects. If this also fails, covariates will be dropped as described in section 9.1. A Poisson model will not estimate the risk difference, so if the initial model fails to converge, the same process of variable removal will be followed, within a log-binomial model framework. The p-value relating to the intervention group parameter as generated by the model estimating the relative risk will be presented.

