9.5. Analysis methods – primary outcome(s)

A template for reporting the primary outcome will be given in a separate template report.

The primary outcome is the proportion of women randomised who experience a live birth at and beyond 34 weeks of gestation. The denominator of this proportion will be all women randomised and the numerator will be those women who have conceived during the six ovulation induction cycles (maximum 240 days) and have gone on to have a live birth at or beyond 34 weeks.

A mixed effects binomial regression model will be used to calculate the risk difference (identity link) and relative risk (log link) with 95% confidence intervals for the primary outcome (live birth \geq 34 weeks), adjusting for the randomisation variables listed in section 4.6. If this primary method doesn't converge, the plan detailed in section 9.1 will be followed.

Statistical significance of the treatment group parameter will be determined (p-value generated) through examination of the associated chi-squared statistic (this will be obtained from the log-binomial model which produces risk ratios).

Summary data of the primary outcome in the form of frequencies and percentages will be produced that looks at the primary outcome for all the combinations of treatments (combinations A-D as per section 6.2 Baseline characteristics).

In the event of babies from a multiple pregnancy having different pregnancy outcomes, if at least one of the babies had a live birth \geq 34 weeks then this will count as a live birth \geq 34 weeks overall. If all those babies within that multiple pregnancy have the same pregnancy outcome (e.g. all are live births) then this will only be counted as one outcome (event).

See section 9.1 for covariate adjustment and model convergence.

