9.6. Analysis methods – secondary outcomes

A template for reporting the secondary outcomes will be given in a separate template report. See section 9.1 for covariate adjustment and model convergence.

Dichotomous outcomes (e.g. pregnancy loss and APGAR score <7) will be analysed using the same regression approach as the primary outcome, using the denominators detailed in section 5.3. Pregnancy events will be limited to those who conceived during the six ovulation induction cycles (maximum 240 days). For pregnancy end outcomes, in the event of babies from a multiple pregnancy having different outcomes, for example one live birth and one miscarriage, both the events will be counted in the separate categories (i.e. they will contribute to both a live birth event and a miscarriage event.

Mixed-effects Poisson regression will be used for count data (number of ovulation induction cycles to live birth) with an Incidence Rate Ratio (IRR) and confidence interval generated (if there is evidence of overdispersion then a negative-binomial model will be fitted instead). This outcome will be reported as count data (i.e. 1, 2, 3, 4, 5, and 6).

For continuous secondary outcome measures (e.g. birthweight and gestational age) means and standard deviations will be reported alongside adjusted mean differences (with confidence intervals) estimated using a mixed effects linear regression model.

A Cox Proportional Hazard (PH) model (provided the assumptions of proportionality are met) will be utilised for time to event data (time from randomisation to pregnancy). Data will be summarised with medians and interquartile ranges and estimates of difference presented as adjusted hazard ratios (with confidence intervals). A Kaplan Meier plot will be produced to assess the data visually. In this model, randomising centre will be regarded as a shared frailty.

Mode of birth will be analysed as unassisted vaginal versus any other category; all categories of data will be presented.

For birthweight, babies from multiple births will be included as separate babies. To allow for the clustering at the mother level a robust variance estimator clustered by mother will be included in the model. If this does not work (e.g. failure to converge) then analysis on the mother's level will be used instead and the outcome interpreted as such.

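### The relative-risk fallback in SAP 9.1 leaves Poisson for a fixed-effects log-binomial model and then drops covariates by a rule that refers to itself; a fixed-effects robust Poisson step would close the gap.

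*SAP*

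**What the plan says.** SAP 9.1 starts from this model: "A mixed effects binomial regression model will be used to calculate the risk difference (identity link) and relative risk (log link"). On the covariates it states: "Randomising centre will be included as a random intercept in the model, and all other factors as fixed effects". Besides centre there are five minimisation factors (SAP 4.6): age, BMI, previous pregnancy, previous clomifene or letrozole exposure, and periods in the preceding six months.

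The relative-risk sequence is then:

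1. Mixed-effects log-binomial.
2. If that fails, "a Poisson regression model with randomising centre as a random effect and robust standard errors will be used to estimate the relative risk".
3. If that fails, "randomising centre will be removed and the log-binomial model will be refit for just fixed effects".
4. "If this also fails, covariates will be dropped as described in section 9.1".

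For the risk difference, Poisson is ruled out and "the same process of variable removal will be followed, within a log-binomial model framework". The primary p-value comes from the model that estimates the relative risk.

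SAP 9.5 only sends the reader back: if the primary model does not converge, "the plan detailed in section 9.1 will be followed". SAP 9.6 extends the approach to dichotomous secondary outcomes, which "will be analysed using the same regression approach as the primary outcome", with the denominators of SAP 5.3.

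**The concern.** There are three weaknesses.

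- **Order of steps.** Poisson is brought in because a log-binomial fit can fail when fitted risks approach 1. If the Poisson fit then fails because of the random centre effect, the natural move is to remove that effect and stay with Poisson. Step 3 instead restores the constraint that fitted risks stay below 1.
- **Undefined rule.** Step 4 sits in section 9.1 and cites section 9.1. Nothing there or elsewhere says which covariate goes first, how many may go, or when to stop. Under SAP 5.6 the statistician may know the codes once the database is locked, so the choice could be made with allocation known.
- **Risk difference.** Its fallback relies on the same undefined removal, inside a log-link model whose coefficients do not directly give a risk difference.

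At stake is pre-specification: adjusted estimates for comparisons A to E could rest on different covariate sets chosen after the event.

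**Working it through.** **Baseline inputs reproduced.** SAP 4.7 gives 760 analysed at 44% v 34% (comparison C, 81% power) and 1,520 analysed at 39% v 29% (A and B, 98.5%). With n per arm and two-sided 5%, power = Φ{[Δ − 1.96√(2p̄(1−p̄)/n)] / √(p₁(1−p₁)/n + p₀(1−p₀)/n)}.

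- C, n = 380: (0.10 − 1.96 × 0.03539)/0.03520 = 0.871, so 80.8%.
- A and B, n = 760: (0.10 − 1.96 × 0.02430)/0.02417 = 2.167, so 98.5%.

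Both agree with the SAP.

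**Where the log link runs out of room (primary outcome).** Assumed covariate prevalences are 20, 40, 35, 30 and 75%. For each set of assumed relative risks, the most favourable covariate pattern relative to the average is (product of the relative risks above 1) / (product of 1 − prevalence + prevalence × RR). Multiplying by 0.44, the highest arm rate in comparison C, gives the largest expected risk, ignoring centre.

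| Assumed effects (RRs) | Ratio | Largest risk |
|---|---|---|
| Weak (0.85, 0.85, 1.15, 0.9, 1.2) | 1.38/1.0705 = 1.289 | 0.57 |
| Moderate (0.6, 0.7, 1.3, 0.8, 1.5) | 1.95/1.1563 = 1.686 | 0.74 |
| Strong (0.4, 0.55, 1.6, 0.7, 2.0) | 3.20/1.3905 = 2.301 | 1.01 |

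Only the strong set reaches 1. With 0.39, the highest arm rate in A, it gives 2.301 × 0.39 = 0.90.

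**Simulated fits, primary outcome.** With 45 centres (Protocol 3.2):

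- The fixed-effects log-binomial failed in 0% of trials at n = 1,520 and n = 760 with a step-halving algorithm and logit covariate effects, and in 0% with the weak and moderate sets above.
- With the strong set, convergence depended on the algorithm. At n = 760 (44% v 34%) it was 96% with a standard package and 27% with plain Fisher scoring. With plain Fisher scoring it was 71% at n = 1,520.
- The fixed-effects Poisson model with robust standard errors and all five covariates converged in 100% throughout. In one run its power was 79–82% at n = 760 and 98–99.7% at n = 1,520, with type I error 3.4–5.4% under the null at n = 760.

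**Simulated fits, common secondary outcomes.** Under SAP 5.3 the denominator is women with a live birth at 24 weeks or later. The SAP rates imply about 1,520 × 0.34 = 517 (A) and 760 × 0.39 = 296 (C) live births at 34 weeks or later, so 540–560 and 300 were used. Outcome rates of 88–95% are assumptions. The headroom is small: 1/0.88 = 1.14 and 1/0.93 = 1.08. Failure of the fixed-effects log-binomial over the assumption sets tried:

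| Outcome | Comparison A | Comparison C |
|---|---|---|
| Live birth ≥37 weeks | 14–70% | 54–74% |
| Singleton live birth ≥34 weeks | 47–86% | 83–93% |

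The fixed-effects Poisson fit failed in 0%. The width of these ranges shows how far the rates move with the assumed covariates and algorithm; they are not bounds.

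**What an open choice could do.** Five covariates allow 2⁵ − 1 = 31 reduced models.

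- Primary outcome, n = 760: significance differed between the 31 models in 7% (weak), 13% (moderate) and 25% (strong) of trials with a true difference. Under the null at least one was significant in 6.6–10.2%. At n = 1,520 significance differed in 1–2%.
- The two secondary outcomes: relative risks across all 32 covariate sets spanned a median of 0.003–0.012 (95th percentile at most 0.024). Standard errors spanned a median of 1.5–5% (at most 10%).

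**The case against.** A reader might infer that step 3 refits the model that has just failed. It does not. Step 1 has a random centre intercept and step 3 has none; family and link are shared, but the model is simpler and, for the primary outcome, it nearly always fits.

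A reader might also take the failure percentages as the chance that covariates are dropped. They are conditional on both mixed models having failed, and nothing in the documents says how often that would happen. If the centre variance in the mixed Poisson is estimated as zero, its point estimates equal those of the fixed-effects Poisson with all five covariates, so step 2 already delivers the wanted fit unless the software reports non-convergence.

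Third, the consequence is limited where failure is most likely. SAP 5.1 provides p-values only for the primary and safety outcomes, so no significance claim for the two live-birth outcomes depends on the covariate set, and their estimates move little.

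These points stand and limit the size of the concern. They do not supply the missing order or stopping rule, and they do not give the risk difference, which is reported for the primary outcome, a workable fallback.

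**Conclusion.** The drafting gap is certain: the dropping rule refers to itself, and SAP 9.6 carries it to the dichotomous secondary outcomes. Its practical size is modest. The primary relative risk and p-value are unlikely to be affected unless covariate effects are strong and the fitting algorithm is fragile; the documents do not support saying that the primary p-value is in practice open to choice. The 7–25% change in significance applies only if step 4 were reached in comparison C.

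For common outcomes among live births, step 3 is a poor choice, with failure in a substantial share of simulated fits under assumed rates and covariates. How often a trial would get that far is unknown and may be small. How often the identity-link model for the risk difference would fail was not simulated, so that part rests on the text alone.

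The change is worth making because a better step is available, it keeps all five fixed minimisation factors, and the SAP's own reference list already contains the modified Poisson method for binary data.

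**What to change.** Replace steps 3 and 4 in SAP 9.1 with:

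> If the mixed Poisson model does not converge, the random centre effect will be removed and a Poisson model with robust standard errors, with all other minimisation covariates as fixed effects, will be fitted; no covariate will be dropped.

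Delete the self-reference to section 9.1. Replace the risk-difference fallback with its own rule, for example: if the identity-link model does not converge, obtain the risk difference by marginal standardisation from the final fitted relative-risk model, with a delta-method or bootstrap interval (name one).

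The cost is wording only. The relative risk remains the target and no new data are needed. The downside is that the robust Poisson interval may be slightly wider where the log-binomial would have converged.

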- Intention to continue current use of metformin treatment for ovulation induction or for other indications;
- Metformin use in the previous 14 days;
- Women opting for alternative methods of ovulation induction or treatment (ovarian stimulation with pituitary suppression using gonadotropins with or without pituitary suppression, e.g. with gonadotropin-releasing hormone [GnRH] agonists, antagonists, or progestogens), or performing intrauterine or intracervical insemination*
- Contraindications to letrozole, clomifene, metformin use and/or pregnancy (see section 7.3 in protocol for full details on contraindications);
- Previous participation in the LOCI trial.

* hCG (Human Chorionic Gonadotropin) trigger injections were listed in the original exclusion criteria but have been removed because the use of ovulation trigger is often considered routine care in participating centres and there is no interaction with the OI treatment.

3. Trial objectives

The primary objectives are:

To test the hypotheses that in women with PCOS and infertility, letrozole versus clomifene, metformin versus placebo, and letrozole plus metformin versus clomifene plus metformin increases the live birth rate (\geq 34 weeks of gestation) by at least 10% (absolute difference). This will involve the following three primary comparisons:

Letrozole vs clomifene

To compare the effectiveness of letrozole vs clomifene in women with anovulatory PCOS and infertility on live birth rate (\geq 34 weeks of gestation).

Metformin vs placebo

To compare the effectiveness of metformin vs placebo in women with anovulatory PCOS and infertility undergoing ovulation induction on live birth rate (\geq 34 weeks of gestation).

Letrozole plus metformin vs clomifene plus metformin

To compare the effectiveness of letrozole plus metformin vs clomifene plus metformin in women with anovulatory PCOS and infertility on live birth rate (\geq 34 weeks of gestation).

4. Trial methods

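### SAP 9.1's fallback for the risk difference names a model whose treatment parameter is a relative risk, so no adjusted risk difference is specified if the identity-link model fails

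*SAP*

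**What the plan says.** SAP 9.1 and 9.5 define two adjusted effect measures for the primary outcome, each with its own link: "A mixed effects binomial regression model will be used to calculate the risk difference (identity link) and relative risk (log link) with 95% confidence intervals". The adjustment set is the minimisation variables of SAP 4.6, with centre as a random intercept. Comparisons A and B also include the other allocation.

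If the binomial model fails, the RR has a chain of alternatives:

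1. "a Poisson regression model with randomising centre as a random effect and robust standard errors will be used to estimate the relative risk"
2. If that fails, "randomising centre will be removed and the log-binomial model will be refit for just fixed effects"
3. "If this also fails, covariates will be dropped as described in section 9.1"

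The RD has a separate sentence. It begins "A Poisson model will not estimate the risk difference, so if the initial model fails to converge" and concludes that "the same process of variable removal will be followed, within a log-binomial model framework".

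The p-value is taken from the model that estimates the RR (SAP 9.1 and 9.5). SAP 3 states the objective as an increase in live birth "by at least 10% (absolute difference"), and SAP 4.7 bases the sample size on the same 10 points.

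**The concern.** The RD sentence sets Poisson regression aside because it does not give an RD, then moves to a log-binomial model, which does not give one directly either. SAP 9.5 itself describes the log-binomial model as the one that yields risk ratios. Neither an identity-link refit nor a standardisation step is mentioned for this outcome. An analyst who follows the text after a failed identity-link fit ends with a second RR and no instruction for obtaining an adjusted RD.

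The covariate-dropping step has a related gap. It sits in section 9.1, refers the reader to section 9.1, and no order of removal appears there. The RR has a Poisson step that keeps centre and all covariates, while the RD goes straight to removal. The two measures could therefore rest on different adjustment sets, with the choice made after seeing which models run.

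At stake is the adjusted estimate on the absolute scale, which is the scale of the objective and of the smallest difference clinicians called important.

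**Working it through.** **1. The plan's own figures.** Inputs from SAP 4.7 (revised sample size): 44% vs 34% with 760 women analysed (comparison C), and 39% vs 29% with 1,520 (comparisons A and B). I assume a two-sided 5% level and the pooled normal approximation without continuity correction:

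power = Φ{[d − 1.96·√(2p̄(1−p̄)/n)] / √[(p₁(1−p₁)+p₂(1−p₂))/n]}

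- C, n = 380 per arm: (0.10 − 1.96×0.0354)/0.0352 = 0.87, giving 80.8% (SAP: 81%).
- A/B, n = 760 per arm: (0.10 − 1.96×0.0243)/0.0242 = 2.17, giving 98.5% (SAP: 98.5%).

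Both reproduce, and neither depends on the RD fallback.

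**2. What each link returns.** I fitted main-effects binomial models to the planned cell rates (24%, 34%, 34%, 44%; 380 women per cell).

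| Model | Treatment result |
|---|---|
| Identity link | RD 10.0 points, SE 2.40, 95% CI 5.3 to 14.7 |
| Log link, coefficient as reported | 0.293, so RR = exp(0.293) = 1.34 |
| Log link plus marginal standardisation | RD 9.9 points, SE 2.40, 95% CI 5.2 to 14.6 |

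The third row follows from the fitted log-link risks. The intercept gives exp(−1.3935) = 0.2482. Multiplying by 1.3406 once gives 0.3327, and twice gives 0.4460. The differences are 0.3327 − 0.2482 = 0.0845 without metformin and 0.4460 − 0.3327 = 0.1133 with it; their mean is 0.0989. The log-binomial fit can therefore supply an RD, but only through a step that the SAP does not prescribe here.

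**3. Why the RR does not stand in for the RD.** RD = base risk × (RR − 1). With RR = 0.39/0.29 = 1.345, the RD is 8.3 points at a base of 24%, 10.0 at 29% and 11.7 at 34%.

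**4. How often the fallback might be reached.** The documents give no covariate effects or prevalences, so these are assumed. All fits below are fixed-effects identity-link binomial models with five binary covariates and 1,520 women. They come from separate runs whose inputs differ somewhat.

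| Assumed covariate effects | Simulated trials | Failure |
|---|---|---|
| Up to ±3 points | 200 | 0% |
| Up to 4 points | 300 | 0% |
| Up to ±5 points, base 24% | 200 | 0% |
| Up to 8 points | 300 | 12% |
| −8 to +8 points, base 22% | 400 | 14.8% |
| Up to ±8 points | 200 | 16.5% |
| A more extreme set | 200 | 38% |

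Adding centre variation to the data in the 12% setting gave 13%. For comparison C (760 women) failure was about 1%. None of these fits included the planned random intercept for centre, so they do not measure the model in the SAP.

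**5. Do the alternatives work?** In the 400-trial run with base 22% and a true RD of 10 points, logistic regression with marginal standardisation converged every time (mean RD 10.2 points, 95% CI coverage 94.8%). Identity-link least squares with robust standard errors also covered 94.8%. In another 400 trials with a true RD of 10 points, the mean RD was 9.7 points from the standardised log-binomial model and 9.9 from the identity link.

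**The case against.** The strongest reply has four parts.

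- **The primary inference does not rest on the RD.** The null hypothesis in SAP 4.8 is no difference in proportions, so 10 points is the design difference and not a tested margin. The p-value comes from the RR model, which has its own fallbacks. Protocol 13.2.1 specifies only an adjusted RR; the RD is a measure added in the SAP. This stands.
- **A crude RD is always available** from the frequencies that SAP 9.5 will tabulate. This also stands, though that RD is unadjusted, whereas SAP 9.1 plans to adjust for the minimisation variables.
- **The wording may be a slip** for an identity-link binomial model, which would keep the RD in the binomial family while terms are removed. That is plausible, but the documents do not settle it, and the sentence would still need correcting.
- **Non-convergence may never occur** for the primary outcome. With modest covariate effects the simulations show no failures. This stands as a limit on the likely impact.

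A reader might also infer that a log-binomial model cannot give an RD at all. That goes too far: step 2 of the working obtains 9.9 points from one by standardisation, and SAP 9.6 already derives marginal differences in proportions from a logit-link model for ovulation rate. The fault is that the step is not stated for this outcome.

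**Conclusion.** The RD fallback in SAP 9.1 is wrong as written and should be fixed. Once the identity-link model fails, the plan specifies no adjusted RD, and the covariate-removal rule is circular and has no order.

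The consequence is limited to the adjusted RD and its confidence interval, on the scale of the 10-point objective. A reader might infer that the primary test or the power is compromised, but the documents do not support that: the RD fallback touches neither the RR, nor its p-value, nor the 81% and 98.5% power. The RR chain shares the unordered covariate-dropping step, but only at its last stage.

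The probability of reaching the fallback is unknown. The range of 0% to 38% rests entirely on assumed covariate effects in models without the centre random intercept. No single value in it should be quoted as the expected failure rate.

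**What to change.** Make two changes to SAP 9.1, before unblinding:

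1. Replace the log-binomial clause with a rule that yields an RD and keeps the minimisation variables. Choose one option in advance: (a) marginal standardisation, with a delta-method or bootstrap 95% CI, from the fitted RR model or from a logistic model with the same covariates; or (b) an identity-link model with robust standard errors. For option (a), say how centre is handled when the predicted risks are averaged.
2. Replace the self-reference with an explicit order of covariate removal, used only as a last resort, and report the adjustment set actually used for each of the RD and the RR.

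The existing RR fallback chain can stay. The cost is one SAP paragraph and a standard post-estimation step in the software the SAP already names. Sample size, data collection and the primary test do not change.
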